#### Sources of Subjects and Recruitment Methods

The Long-Term Follow-Up Study (LTFU) is an NIH-funded multi-institutional study of individuals who were diagnosed before 21 years of age with leukemia, CNS malignancies, Hodgkin's disease, non-Hodgkin's lymphoma, Wilm's tumor, neuroblastoma, soft tissue sarcoma, bone cancer or serious illness who survived at least five years after diagnosis. Eligible participants for the LTFU were identified through medical records and clinic lists at participating centers in the U.S., yielding a retrospectively ascertained cohort of adult childhood survivors with ongoing, longitudinal follow-up. The LTFU includes individuals diagnosed with cancer or serious illness between 1970-1999, recruited from over 25 pediatric oncology institutions in North America. Eligible participants for our study include 21,841 LTFU participants who are still alive and have available contact information.

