### Intervention Assignment and Randomization

#### Pilot Trial

The CCSS Coordinating Center LTFU study staff will randomly select 80 participants among the LTFU cohort (original and expanded together). To do this, CCSS will use stratified random sampling, where we will divide the sample of LTFU participants into two groups: residing in a Medicaid expansion state or not. Random samples will then be selected from each of the two strata until 80 participants are consented and enrolled. The 80 selected participants will be randomized to either enhanced usual care (n=40), or the health insurance navigation intervention (n=40). After obtaining informed consent, participant information will be sent securely to [name] via SharePoint, an encrypted system used to transfer data. [name] team will lead the pilot trial procedures.

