#### **Quantitative Data**

For quantitative data, [name] team at HCI will conduct the analyses with input from [name] and her study team, and the LTFU study team. As discussed in Participants, we will sample by Medicaid expansion vs. non-expansion states. All analyses will be weighted using inverse sampling probabilities so that results are representative of the overall LTFU study cohort.

At baseline, all pilot participants will complete a baseline. The HINP navigator will use each participant's baseline survey responses to personalize and individualize sessions. At the 3-month post-program follow-up, participants will complete the Phase 1 survey Outcome questions, which will be asked within the 5-month time frame period after trial enrollment. Participants will also be asked questions below about feasibility and acceptability.

We will use descriptive statistics to report on the following endpoints: intervention feasibility (percent of participants enrolled), acceptability (satisfaction, perceived support) and efficacy (e.g., ACA familiarity, health insurance literacy, intention to adhere to recommended survivorship care, provider communication, and coverage status).

Descriptive statistics will examine group differences at baseline; any imbalances will be adjusted. We will use chi square and independent t-tests to compare end-of-intervention changes in preliminary efficacy outcomes between the two groups. Although a 3-month post intervention follow-up period is brief, we will also conduct exploratory comparisons with other study outcomes to see if trends change in the expected direction. We will compare pre/end-of-treatment, within groups, with paired t-tests. In addition, we will use bivariate statistics to examine sociodemographic and cancer-related factors (type of

diagnosis, age at diagnosis, years since diagnosis, cancer treatment, chronic conditions, cancer treatment (e.g., cranial radiation yes/no, anthracycline exposure yes/no) associated with feasibility, acceptability and preliminary efficacy outcomes.

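### All analyses are to be weighted by inverse sampling probability, but the plan names chi-square and t-tests without a variance method suited to weights

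*Combined protocol and SAP*

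**What the plan says.** All references are to the combined protocol and SAP.

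- **Weighting** (VI. Biostatistical Analysis, Quantitative Data): "All analyses will be weighted using inverse sampling probabilities so that results are representative of the overall LTFU study cohort". No analysis is exempted.
- **Between-arm tests** (same section): "We will use chi square and independent t-tests to compare end-of-intervention changes in preliminary efficacy outcomes between the two groups".
- **Within-arm tests** (same section): "We will compare pre/end-of-treatment, within groups, with paired t-tests". The section also mentions adjustment for baseline imbalance and bivariate statistics, without naming a method for either.
- **Sampling** (IV. Subject Enrollment, Pilot Trial): "we will divide the sample of LTFU participants into two groups: residing in a Medicaid expansion state or not", and then "Random samples will then be selected from each of the two strata until 80 participants are consented and enrolled". Those enrolled are randomised 40 to each arm.
- **Frame** (III. Subject Selection, Sources of Subjects and Recruitment Methods): "Eligible participants for our study include 21,841 LTFU participants who are still alive and have available contact information".

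The documents do not give the number to be enrolled per stratum, the cohort's split by expansion status, the scaling of the weights, a variance estimator or a survey procedure. They state no alpha, power, effect size or standard deviation either.

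**The concern.** The usual formulas for a t-test and a Pearson chi-square let each person count once with equal weight. With unequal weights, the variance of a weighted mean depends on the squares of the weights, and the ordinary formulas leave that out. An analyst who applies the weights and then runs the tests as named would get standard errors that are too small and p-values that are too favourable. This would affect health insurance literacy and financial distress, the two outcomes in the A2b hypothesis, as well as the other efficacy comparisons.

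A second, separate issue is precision. Unequal weights widen the interval for the comparison of navigation with enhanced usual care even when the variance is computed correctly. In return, the estimate refers to the whole cohort and not only to those enrolled. The plan does not acknowledge this exchange or provide an unweighted result to set beside the weighted one.

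**Working it through.** **Plan's own figure.** The sample size of about 40 per arm comes without a power calculation, so there is nothing to reproduce. For orientation, at two-sided 5% (assumed), 40 per arm gives 80% power for a difference of 0.63 SD.

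**Inputs.** From the documents: 80 enrolled, 40 per arm, two sampling strata, weights in all analyses. Assumed because not stated: the fraction *f* of the 80 in the expansion stratum, the fraction *P* of the cohort in expansion states, two-sided 5%, no dropout, and no stratum or treatment effect in the null simulation.

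**Step 1, design effect.** Kish's formula is n·Σw²/(Σw)². With two strata it becomes

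DEFF = P²/f + (1 − P)²/(1 − f).

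For f = 0.5 this is 2[P² + (1 − P)²]. Two examples:
- P = 0.60: 2(0.36 + 0.16) = 1.04
- P = 0.80: 2(0.64 + 0.04) = 1.36

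Effective n is 80/DEFF, and a correctly computed interval widens by √DEFF.

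**Step 2, false-positive rate of the ordinary formula.** With weights rescaled to sum to 80, the ordinary standard error is too small by a factor of about √DEFF. The nominal 5% test then rejects with probability of about 2[1 − Φ(1.96/√DEFF)]. For P = 0.80, 1.96/1.166 = 1.681, which gives 9.3%.

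**Step 3, simulation.** There were 10,000 null trials per scenario with 40 against 40, a normal outcome and a 30% binary outcome. All rows have 40 per stratum.

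| P | DEFF | Effective n | Interval wider by | Formula | Weighted t, ordinary SE | Weighted chi-square, ordinary | Weighted t, robust SE |
|---|---|---|---|---|---|---|---|
| 50% | 1.00 | 80 | 0% | 5.0% | 4.8% | 5.1% | 4.8% |
| 60% | 1.04 | 77 | 2% | 5.5% | 5.2% | 6.2% | 4.8% |
| 65% | 1.09 | 73 | 4% | 6.1% | 5.9% | 6.2% | 5.1% |
| 70% | 1.16 | 69 | 8% | 6.9% | 6.8% | 7.1% | 5.1% |
| 80% | 1.36 | 59 | 17% | 9.3% | 9.9% | 9.5% | 5.9% |

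Other simulation runs put the 80% t-test figure at 9.4 to 9.5%, so about 9.5% is a fair summary of the upper end.

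**Step 4, other splits.**
- Strata of 60 and 20 with P = 60%: DEFF = 0.36/0.75 + 0.16/0.25 = 1.12. The t-test rejects in 6.3% of null trials and the chi-square in 6.5%.
- Strata of 56 and 24 with P = 70% (proportional): DEFF = 1.00, and the ordinary tests hold their level.

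**Step 5, power cost of weighting with a correct variance.** At 0.63 SD and 40 per stratum, power falls from 80% to 79%, 74% and 68% for P = 60, 70 and 80%.

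**The case against.** The strongest reply has four parts.

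**The plan names test families, not formulas.** Weighted and design-based versions of the t-test and chi-square exist, and the section that names the tests also requires weights. This stands. A reader might infer that the plan prescribes wrong standard errors, but the text does not go that far. What it lacks is any statement of the variance method, so nothing rules out the ordinary formulas.

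**The size depends on unstated inputs.** This also stands. At 60 to 65% the inflation is about a point or less, and under proportional sampling with rescaled weights it is nil. The stated reason for weighting, that results should represent the cohort, hints at unequal sampling rates but does not establish them.

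**The weights serve a purpose.** A reader might infer that weighting the randomised contrast is pure waste, since randomisation already makes the unweighted contrast valid. The documents do not support that. If the effect differs by expansion status, the unweighted contrast estimates the effect in the enrolled sample, whereas the plan says it wants results that represent the cohort. The extra variance is the price of that target.

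**This is a pilot.** Efficacy is called preliminary and is listed under Secondary Outcomes. That limits the impact but does not remove it, because Aim 2 (A2b) calls two of these outcomes primary, with a directional hypothesis.

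A reader might also imagine raw weights being entered as case counts, which would be far more damaging. No section suggests this. Nor can the mean weight be obtained by dividing the frame of 21,841 by 80: selection continues until 80 have enrolled, so the number selected, which sets the sampling probability, is unknown.

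**Conclusion.** The point holds as an omission. The plan requires weights everywhere, names chi-square and t-tests, and gives no variance method suited to weights. Used in their ordinary form with rescaled, unequal weights, these tests understate the standard error. Assuming 40 per stratum and 60 to 80% of the cohort in expansion states, the design effect is 1.04 to 1.36 and the false-positive rate about 5 to 9.5%, against 4.8 to 5.9% with a robust variance. Weighting the between-arm contrast widens its interval by 2 to 17% over the same range, in exchange for a cohort-average target. Both effects vanish if sampling is proportional and the weights are rescaled. Severity is minor to moderate.

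**What to change.** Amend the Quantitative Data section as follows.

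1. For every weighted analysis, replace the plain t-tests and chi-square with survey-weighted regression using robust (linearised) standard errors and with the Rao-Scott chi-square. Treat the within-arm changes in the same way.
2. Beside the weighted between-arm contrast, report an unweighted contrast adjusted for the Medicaid-expansion sampling stratum. State that the weighted one targets the cohort-average effect, and the unweighted one the effect in the enrolled sample, with better precision when the weights are unequal.
3. State the planned number per stratum, the cohort's split, and how the weights are formed and scaled, so that the design effect can be calculated beforehand.

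The cost is some wording and standard software, with no new data or visits. Some p-values will become slightly less favourable. Reporting two contrasts also means saying in advance how each will be read.

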## Outcomes

### Primary Outcomes: Feasibility and Acceptability.

1. Feasibility: Number of eligible enrollees and number of sessions completed. 2. Acceptability: 4-point scales of satisfaction with navigation services (To what extent has this program met your needs? Did you get the kind of health insurance assistance that you wanted? How helpful has this program been for you?) and perceived support (emotional/informational scale of the Medical Outcomes Study social support survey, an 8-item scale widely used with cancer patients).

### Secondary Outcomes: Efficacy.

The ACS's National Patient Navigator Leadership Summit recommend patient-navigation outcome measures, which included: perceived knowledge, perceived confidence in overcoming barriers to care, and satisfaction with patient navigation services. Accordingly, we will measure: 1) health insurance literacy, 2) financial distress related to medical costs.

3) familiarity with healthcare reform policies, 4) insurance status (among those insured at study enrollment), and 5) discussion with providers about health care costs and preventive services among those having a visit during this interval (2-item y/n questions).

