### **c. Rationale of Proposed Research**

Health care reform under the Patient Protection and Affordable Care Act (ACA) offers considerable opportunities for childhood cancer survivors to obtain coverage and improve access to needed care. However, in the general population, many people have low understanding of available insurance benefits and resources, and have limited health insurance literacy (i.e. perceived knowledge, ability, and confidence to make informed decisions about choosing and using health insurance). Misperceptions about which services require out-of-pocket costs may lead some enrollees to avoid services that are in fact exempt from cost sharing. Even with coverage protections from the ACA, barriers to obtaining quality coverage (e.g., in states without Medicaid expansion) and accessing needed care may remain for childhood survivors. Understanding and navigating insurance benefits is crucial for cancer survivors to obtain the health care they need. In this new post-reform landscape, the degree to which coverage and costs have changed for childhood cancer survivors is still largely unknown.

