### **Aim 2: To conduct a videoconferencing-based pilot randomized trial of the HINP (n= approximately 80).**

A2a: To assess the feasibility (number of eligibles enrolled and sessions completed) and acceptability (satisfaction, perceived support) of participants undergoing the HINP.

A2b: At 3-month post-program follow-up, to assess the efficacy of the HINP to assist participants with accessing and utilizing coverage and managing costs. Primary

outcomes are 1) health insurance literacy and 2) financial distress related to medical costs

**A2b Hypothesis:** The HINP, compared to enhanced usual care, will improve participants' health insurance literacy and decrease financial distress.

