## **Phase 2**

### Pilot Trial Design

We will recruit and randomize approximately 80 LTFU participants to a health insurance navigation intervention or to enhanced usual care (Please see Sections III and IV for information on subject selection and consenting procedures). We have selected this sample size of approximately 40 per arm to enable evaluation of feasibility and acceptability goals as well as explore meaningful differences in the outcomes. Surveys will be conducted at baseline and 3-month post program completion follow-up via REDCap or mail. All participants will be asked to complete a follow-up survey approximately 3-months after the HINP intervention period (in other words approximately 5-months post pilot trial enrollment).). After completion of the follow-up survey, HINP participants will be contacted for an exit interview (see Phase 3 below). Participants will be remunerated \$20 for each survey and the exit interview by the University of Utah

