#### Proposed Navigation Intervention Structure and Content

The program will be delivered via videoconferencing by a navigator over a 1-month period. Accordingly, patient navigation is delivered until the desired endpoint is achieved; we propose that this will be accomplished with 4 navigation sessions (See Table 1: Proposed HINP Intervention). The proposed program content was informed by: 1) aforementioned research identifying childhood survivors' difficulties with accessing and utilizing one's coverage and managing costs, 2) CCSS health insurance survey, and 3) ACA provisions that are relevant to survivors (e.g., prevention services exempted from cost sharing, sources of available coverage and eligibility, benefits policies that have cost-related implications like OOP costs, and essential health benefits such as prescription medications. Based on advisory board and individual interview feedback, the content and tailoring of information will be modified.

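### The provider-discussion outcome is compared only among people who had a visit after randomisation, which the program may itself change; an all-randomised figure should stand beside it (minor)

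*Combined protocol and SAP*

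**What the plan says.** Section VI, Secondary Outcomes: Efficacy, lists five outcomes. The fifth is discussion with providers about health care costs and "preventive services among those having a visit during this interval (2-item y/n questions". That section does not spell out the interval. Pilot Trial Design places the follow-up survey about 3 months after the intervention period, "in other words approximately 5-months post pilot trial enrollment", and the Quantitative Data section uses the same 5-month frame.

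The Quantitative Data section counts this topic among the efficacy endpoints to be described: "intention to adhere to recommended survivorship care, provider communication, and coverage status". For the test between arms it says: "We will use chi square and independent t-tests to compare end-of-intervention changes in preliminary efficacy outcomes between the two groups". On adjustment it says: "Descriptive statistics will examine group differences at baseline; any imbalances will be adjusted". It also weights all analyses by inverse sampling probability. It plans no figure for this outcome over all randomised participants, and no comparison of visit rates over the same interval. The Outcome Measures list does include provider visits, but over the past year.

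Several places give a reason why visiting might depend on arm:

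- The Rationale says: "Misperceptions about which services require out-of-pocket costs may lead some enrollees to avoid services that are in fact exempt from cost sharing".
- Aim 2b is "to assess the efficacy of the HINP to assist participants with accessing and utilizing coverage and managing costs".
- The intervention content includes "prevention services exempted from cost sharing, sources of available coverage and eligibility".
- The first session in Table 1 is about survivorship healthcare needs.

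**The concern.** Randomisation makes the two arms comparable as they stand at enrolment. It does not make the visitors in one arm comparable with the visitors in the other if the program brings extra people to a provider. The fourth secondary outcome shows the contrast: it is restricted by insurance status at enrolment, a baseline condition that leaves the randomised comparison intact. The fifth is restricted by something that happens afterwards. Adjusting for baseline imbalance and weighting back to the cohort do not address this.

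At stake is the direction of the estimate. If the program brings in people who seldom raise costs or prevention, the among-visitors figure falls although nobody discusses less. If it brings in people who came in order to ask, the figure rises although regular attenders have not changed. A small real gain could likewise be hidden or inflated.

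**Working it through.** The plan has no figure to reproduce here: it gives no visit rate, discussion rate or effect size for this outcome. Only the 40 per arm comes from the documents. The rest is assumed and shown as a range.

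**Inputs**

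- v, the proportion of controls with a visit: 0.60 to 0.80 (assumed).
- Discussion rate among regular attenders, meaning those who would visit in either arm: 0.40 in both arms, so no true change among them (assumed).
- x, the rise in visiting due to the program: 0.05 to 0.20, with nobody deterred from visiting (assumed).
- q, the discussion rate among added visitors: 0.10, 0.40 or 0.70 (assumed).
- Survey return: 100% or 80% (assumed).
- Sampling weights are ignored; unequal weights would usually widen the intervals.

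**Artefact among visitors**

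Intervention rate = (0.40v + xq)/(v + x). Subtracting the control rate of 0.40 gives artefact = x(q − 0.40)/(v + x). If q = 0.40 or x = 0, it is zero. For q = 0.10 or 0.70 its size is 0.30x/(v + x):

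- Smallest: v = 0.80, x = 0.05: 0.015/0.85 = 1.8 points.
- Largest: v = 0.60, x = 0.20: 0.06/0.80 = 7.5 points.
- x = 0.10: 0.03/0.70 = 4.3 points (v = 0.60) and 0.03/0.90 = 3.3 points (v = 0.80).

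**All randomised, no visit counted as no discussion**

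Control = 0.40v; intervention = 0.40v + xq. With x = 0.10:

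| v | q | Among visitors, control v intervention | All randomised, control v intervention |
|---|---|---|---|
| 0.60 | 0.10 | 40% v 36% | 24% v 25% |
| 0.60 | 0.70 | 40% v 44% | 24% v 31% |
| 0.80 | 0.10 | 40% v 37% | 32% v 33% |
| 0.80 | 0.70 | 40% v 43% | 32% v 39% |

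In the first and third rows the two figures point in opposite directions.

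**Precision**

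Half-width = 1.96 × √[p0(1 − p0)/n0 + p1(1 − p1)/n1]. With v = 0.60, x = 0.10, q = 0.10 and full return, n0 = 24 and n1 = 28:

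1.96 × √(0.24/24 + 0.357 × 0.643/28) = 0.264.

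With v = 0.80 and the same x and q, n0 = 32 and n1 = 36, and the result is 0.232. At 80% return, multiply by 1/√0.8 = 1.118. Over the whole grid the among-visitors half-width is 22.4 to 30.5 points. For all randomised with x = 0.10 it is 19-21 points at full return and 21-23 at 80%.

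**Chance that the estimate takes the artefact's sign**

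Φ(artefact/SE), where SE = half-width/1.96. For v = 0.60, x = 0.10, q = 0.10 at full return: SE = 0.264/1.96 = 0.135, and Φ(0.0429/0.135) = 0.625.

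- x = 0.10, full return: 61-63%.
- x = 0.10, 80% return: 60-61%.
- Whole grid (x = 0.05 to 0.20, both return rates): about 55-72%.

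**A real 5-point gain among regular attenders**

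Observed difference = (0.45v + xq)/(v + x) − 0.40. For x = 0.10 it shows as 0 to 1.1 points (q = 0.10) or 7.8 to 8.6 points (q = 0.70). Over x = 0.05 to 0.20 the ranges are −3.8 to 2.9 and 6.5 to 11.3 points.

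**The case against.** The best case for the plan is that people cannot discuss anything with a provider they have not seen, so restricting the item to those with a visit is an ordinary condition. The outcome is fifth of five, is primary nowhere, and sits in a pilot sized for feasibility and acceptability. No decision rule uses it. The rates and the gap between added and regular visitors are assumed, and the documents make an effect on visiting plausible without stating one. The all-randomised figure answers a different question: at v = 0.60, x = 0.10, q = 0.70 it moves 7 points with no change among regular attenders, because it includes uptake.

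Most of this stands, and it sets the grade. It does not remove the selection problem. The among-visitors figure can be kept, but it should not be read as a randomised comparison. The past-year visit item does not fill the gap: asked about 5 months after enrolment, it reaches back about 7 months before enrolment.

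Four stronger readings might be inferred, and the documents do not support them:

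- That the unnamed interval is an error in itself. The 5-month frame is the natural reading, and the survey wording, where a look-back would normally sit, is not in the supplied text.
- That the planned contrast is biased. It is biased only if visit rates or visitor mix differ by arm.
- That this outcome will certainly be tested only among visitors. The Quantitative Data section names provider communication without a visit restriction, and it separates preliminary efficacy outcomes from exploratory comparisons without saying where this item falls. It states no all-randomised denominator either.
- That one sign probability, such as 61-63%, is the general result. That range belongs to a 10-point rise at full survey return.

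**Conclusion.** The concern holds as a minor one. The outcome is defined on a post-randomisation event that the program plausibly affects, and no all-randomised figure or same-interval visit comparison is planned beside it. On the assumed inputs the artefact is 1.8 to 7.5 points either way, well inside half-widths of about 22-31 points, and it tilts the sign of the estimate to about 55-72% instead of 50%. It would be zero if added visitors discussed as often as regular attenders, or if the program changed neither the number nor the mix of visitors. The pilot's feasibility, acceptability, insurance literacy and financial distress results are untouched. Only the direction read from this one outcome is affected.

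**What to change.** In Section VI:

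1. Add a between-arm comparison of each of the two items among all randomised participants who return the follow-up survey, counting no visit as no discussion.
2. Report by arm the proportion with a visit in the same interval.
3. Keep the among-visitors figure, labelled descriptive and not a randomised comparison.
4. As part of this, state that the interval runs from enrolment to follow-up in both arms.

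The cost is one definition and one added analysis on survey data, with no extra participants or contacts. If the survey uses another look-back, or does not record whether a visit took place in this interval, the item needs rewording. The downside is that the all-randomised figure mixes visit uptake with discussion, so it must be read beside the other two.
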